### 8.2.14 Questionnaires

The questionnaires will be administered to the participants using paper questionnaires and/or an electronic data collection system. The questionnaires will be asked according to Section 8.5.

#### 8.2.14.1 **PHQ-9 -- The Patient Health Questionnaire**

The Patient Health Questionnaire PHQ-9 for Depression will be used to screen for current (within 2 weeks) depression. Potential participants who score >9 (or who score >0 on item #9 ("Thoughts that you would be better off dead, or of hurting yourself in some way")) will be excluded from study participation, and, at the discretion of the study physician/physician assistants, referred to appropriate psychiatric treatment. Participants will respond to this questionnaire at all visits. This questionnaire will be administered at every visit, including the screening visit (V1 through V7).

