### 3.3 POINT OF ENROLLMENT

Participants will be enrolled after all safety laboratory results have been received and reviewed by the medical staff (MD or PA). The Halo G6 and the cartomizers will be dispensed starting at V2, and at each subsequent visit until the End-Of-Study. Study drugs will be dispensed starting at V3, and at each subsequent visit until the End-Of-Study.

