#### 4.1.2 Exclusion Criteria

Potential participants who show or report indications of or self-report a diagnosis of conditions listed below may be excluded from the study. If the study physician (or designee) determines through the course of pre-screening, or a physical screen, medical history, physical findings, current medications, ECG, or laboratory findings suggests one of the conditions listed below, or findings reveal other information that may potentially jeopardize the participants' safe participation, then they may be excluded. For medical conditions that do not appear below,

the participant may be enrolled if the study physician (or designee) does not feel that the medical condition would jeopardize safe study participation or data validity.

Exclusion Criteria
1. Is unhealthy or cannot participate in the study for any reason (e.g., medical, psychiatric, and/or social reason) as judged by the Investigator or designated medical staff based on all available assessments from the screening period (e.g., safety laboratory, vital signs, physical examination, ECG, concomitant medications and medical history).
2. PHQ-9 score greater than 9, or a score greater than 0 on item #9 (“Thoughts that you would be better off dead, or of hurting yourself in some way”) at screening.
3. Planned use of an FDA-approved smoking cessation product during the study.
4. High blood pressure (systolic > 150 mmHg or diastolic >95 mmHg) at screening.
5. Body mass index (BMI) less than 15.0 kg/m  or greater than 40.0 kg/m  .
6. Coronary heart disease, structural cardiac disease (including, but not limited to valvular heart disease or cardiac murmurs), cardiac dysrhythmias, syncope, cardiac chest pain, or history of heart attack or heart failure.
7. Has received psychotherapy or behavioral treatments potentially impacting symptoms of depression, anxiety, or nicotine withdrawal within 30 days of screening, or during the study.
8. Taking antidepressants, psychoactive medications (e.g. antipsychotics, benzodiazepines, hypnotics) or medications that prolong QT c .
9. Use of any of these products in the past 30 days: 
 
a. Illegal drugs (or if the urine drug screen is positive for cocaine, THC, amphetamines, methamphetamines, or opiates);
 
b. Experimental (investigational) drugs that are unknown to participant;
 
c. Chronic opiate use.
 

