### 8.2.5 Electrocardiogram (ECG)

ECG recording will be performed as per the site's standard operating procedures. A standard 12-lead ECG will be recorded after the participant has rested for at least 5 minutes in a supine position.

The following parameters will be documented: heart rate, PR interval, QRS interval, QT interval, and QTc interval. Every ECG will be assessed as normal, abnormal – not clinically significant, or abnormal – clinically significant.

ECG print-outs will be interpreted by a qualified physician or licensed medical provider. Any print-outs of ECGs on thermo-sensitive paper must be photocopied and stapled together for inclusion in the source documents and signed by the Investigator or designee.

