## 8.5 SCHEDULE OF EVENTS

Visit Assessments and Procedures		Screening Session	Baseline Cig Data Collection	Laboratory Sessions							Product Use Period
				V2	V3	V4	V5	V6	V7	13 Weeks	
		V1								PM SMS	
Informed Consent and Guidance		•									
Inclusion/Exclusion Criteria		•									
Enrollment/Randomization				•							
Prior and Concomitant Medication		•		•	•	•	•	•	•		
Questionnaires	Smoking History Questionnaire	•									
	Registration Form	•									
	Employment History			•							
	Medical History/Review of Systems	•									
	Payment Verification Form	•		•	•	•	•	•	•		
	Reasons to Smoke			•					•*		
	Modified Cigarette Evaluation Questionnaire Extended (mCEQE)			•	•	•	•	•	•		
	Modified e-Cigarette Evaluation Questionnaire Extended (meCEQE)				•	•	•	•	•		
	The Fagerström Test for Nicotine Dependence (FTND)			•	•				•		
	Shiffman-Jarvik Withdrawal Scale			•	•	•	•	•	•		
	Assessment of Behavioral OUTcomes (ABOUT)			•	•				•		
	Patient Health Questionnaire (PHQ-9)	•		•	•	•	•	•	•		
	e-Cigarette Usage and Smoking Status (via daily SMS text)			•						•	
	Medication Adherence (via daily SMS text)									•	
	Safety Laboratories		•								
Serum Pregnancy Test (Females)		•									
Urine Pregnancy Test (Females)				•	•	•	•	•	•		
Urine Drug Screen		•									
CO Breath Test		•		•	•	•	•	•	•		
ECG		•									
Vitals	Blood Pressure	•		•	•	•	•	•	•		
	Heart rate	•		•	•	•	•	•	•		
	Temperature	•									
	Respiratory rate	•		•	•	•	•	•	•		
	Weight	•		•	•	•	•	•	•		
	Height	•									
Physical Examination		•		•#	•#	•#	•#	•#	•#		
Halo Assessment and Questionnaire				•							
Collect Used/Unused Halo products					•	•	•	•	•		
Dispense Halo products				•	•	•	•	•			
Collect Used/Unused Blister Packs					•	•	•	•			
Dispense Study Drugs in Blister Packs					•	•	•	•			

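### PHQ-9 is repeated through V7, but its cut-offs apply only at entry; no rule requires the form to be read before drug is dispensed at V3-V6 or says how to respond to a positive item 9

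*Combined protocol and SAP*

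**What the plan says.** **Entry rule.** Section 4.1.2, item 2 excludes anyone with "PHQ-9 score greater than 9, or a score greater than 0 on item #9", and ties this to screening. Section 8.2.14.1 repeats the cut-offs for prospective participants, who are excluded and may be referred for psychiatric care at the medical staff's discretion.

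**Repeat use.** Section 8.2.14.1 continues: "This questionnaire will be administered at every visit, including the screening visit (V1 through V7"). The row "Patient Health Questionnaire (PHQ-9") in Section 8.5 is marked at V1 to V7. Section 8.2.14 gives the mode of completion: "The questionnaires will be administered to the participants using paper questionnaires and/or an electronic data collection system".

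**Dispensing.** Section 3.3: "Study drugs will be dispensed starting at V3, and at each subsequent visit until the End-Of-Study". In Section 8.5 the row "Dispense Study Drugs in Blister Packs" is marked at V3 to V6. Sections 6.4.1 and 7.4.1 let the investigator or designated staff dispense, and mention no mood check.

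**Known risk.** The Precautions in the participant instructions for both bupropion and zonisamide list depression and suicidal thoughts among reported effects.

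**The concern.** The protocol treats any item 9 score above zero as a bar to entry. It then asks the same question at each later visit and states no consequence. If the plan is followed exactly, a participant whose V3 answer would have barred entry can be given both drugs at that visit, although their own handouts warn of suicidal thoughts. Item 9 is the only question in the appended forms that asks about self-harm. The form is self-completed, so a positive answer is seen only if someone reads it. At stake is a participant's safety, using information already on site.

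**Working it through.** The plan gives no figure to reproduce here. The check sets the sections side by side, with some counting.

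**1. What is stated, by visit**

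| Visit | PHQ-9 given | Study drug dispensed | Stated consequence of a positive form |
|---|---|---|---|
| V1 | yes | no | exclusion, discretionary referral |
| V2 | yes | no | none |
| V3 | yes | yes (first) | none |
| V4-V6 | yes | yes | none |
| V7 | yes | no | none |

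The gap before dispensing therefore covers V3 to V6. The missing response to a positive item 9 covers V3 to V7. V2 is equally silent, but no study drug is given then.

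**2. Time from the entry check to the first dose**

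Inputs: V2 up to 30 days after V1 (4.8.1); V3 after one week of e-cigarette use (3.1); other visits within four days either side (4.8.2).
- Latest nominal V3: 30 + 7 = 37 days after V1, just over five weeks.
- With the window: 37 + 4 = 41 days.

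The PHQ-9 looks back two weeks (Appendix 1), so a screening form can be well out of date at the first dose.

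**3. Whether the next form would catch a missed answer**

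Inputs: a 12-week dosing period (6.2), so 84 days from V3 to V7, with four intervals.
- Mean gap: 84 / 4 = 21 days.
- Days not covered by the next form's look-back, per interval: max(0, gap - 14).
- The mean of this is at least 21 - 14 = 7 days, and exactly 7 only if no interval is shorter than 14 days.
- The text does not give single intervals. With assumed gaps of 7, 21, 28 and 28 days: (0 + 7 + 14 + 14) / 4 = 8.75 days.

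Thoughts that had eased before the next look-back began would not reappear on the next form.

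**4. Workload at full retention**
- Forms at V3-V7: 5 x 25 = 125; 5 x 50 = 250.
- Dispensing visits V3-V6: 4 x 25 = 100; 4 x 50 = 200.

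These are upper limits on work. They do not measure risk.

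**5. Possible effect of the fix on the go/no-go rule**

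Section 13.1.1 counts participants lost to follow-up as not switched. Let f be the number of extra certain non-switchers in the first 25, and p the true switching rate (an assumption). The chance of advancing is

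P(X1 >= 16) + sum over k = 13, 14, 15 of P(X1 = k) x P(X2 >= 28 - k),

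with X1 ~ Bin(25 - f, p) and X2 ~ Bin(25, p).

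| p | f = 0 | f = 1 |
|---|---|---|
| 0.60 | 73.5% | 66.2% |
| 0.64 | 87.8% | 82.8% |
| 0.65 | 90.3% | 85.9% |

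Put another way, the stage 1 requirement of 16/25 = 64% becomes 16/24 = 66.7% among the others with one such person, and 16/23 = 69.6% with two.

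**The case against.** The strongest reply is that general provisions already cover this.
- Section 8.2.13 assesses adverse events by questionnaire and interview and refers to Section 8.5. That schedule has no separate adverse-event questionnaire, so the PHQ-9 can fairly be read as one of those meant, although Section 11.2 names interviews only.
- Section 11.2.1 requires new clinically relevant findings to be recorded.
- Section 8 promises medical advice on findings and adherence to SOPs.
- Section 4.4.1 makes discontinuation mandatory for an unsafe condition or when it is in the participant's best interest.
- Section 8.5 allows targeted examinations as needed.
- Section 9.2 provides medical monitoring, dose modification or termination of study drugs, and a 24-hour number.

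Much of this stands. A reader might infer that the protocol has no answer at all to a positive item 9, and the documents do not support that. What these routes lack is a trigger. Each works once somebody has noticed the answer or the participant raises it; none requires the form to be read at that visit or ties it to dispensing.

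A reader might also infer that the PHQ-9 was singled out, because laboratory results and ECGs have named reviewers. That does not follow. Both tests are scheduled at V1 only, and at V1 the PHQ-9 also involves medical staff through the referral decision.

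Finally, treating V3 more strictly than V4-V7 is a judgement. Participants have already used the e-cigarette for a week by V3, so withdrawal may have begun. The case for the split is that V3 is the last point before any exposure to drug, and a hold there only re-applies the sponsor's own entry rule until an assessment is made.

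**Conclusion.** The concern holds as a gap in protocol wording with a direct bearing on participant safety, and it should be fixed. The entry cut-off is not re-applied at the first dose, which can come five weeks or more after screening. From V3 on, nothing requires the form to be read before drug is dispensed or sets a PHQ-9-specific response to item 9.

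Three limits apply. The documents give no rate of positive scores, so the counts of forms and hand-outs should not be read as participants at risk. The time left uncovered between forms can be stated only as at least 7 days on average, assuming the nominal 84 days. Site SOPs are not in the documents and may already contain the step, so confidence is high about the protocol's silence but not about what happens on site.

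A reader might extend the point to the primary result. Nothing supports that: the switching outcome and its test do not use the PHQ-9 after entry.

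**What to change.** Amend Sections 8.2.14.1 and 3.3, and add a footnote to the PHQ-9 row of Section 8.5:

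1. Visit staff score the PHQ-9 before dispensing at V3-V6, and before the participant leaves at V7.
2. At V3, if item 9 is above 0 or the total is above 9, drug is withheld until the MD/PA has made and documented an assessment, with referral as needed.
3. At V4-V7, any item 9 above 0 goes to the MD/PA the same day, is assessed and documented, and is recorded as an adverse event if new.
4. At V4-V7, a total above 9 leads to a documented MD/PA decision on continuing. It should not be an automatic stop, because Section 9.1.4 expects withdrawal to affect mood, concentration and appetite, which the PHQ-9 also scores.

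The cost is protocol wording, one footnote and brief scoring by visit staff. Only flagged forms need MD/PA time. No section places an MD/PA at every visit and there are two sites, so one must be reachable on visit days; the drug handouts already make a study physician available by the 24-hour line. A few participants may not start or continue drug, and would count as non-switchers if they leave. One such person in the first 25 could lower the chance of advancing by 73.5 - 66.2 = 7.3 percentage points at an assumed true rate of 60%, or 90.3 - 85.9 = 4.4 points at 65%. That should be accepted openly; it is no reason to leave a positive item 9 unread.

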#### 8.2.14.2 ***Modified Cigarette Evaluation Questionnaire-Extended (mCEQ-E) and Modified Electronic Cigarette Evaluation Questionnaire-Extended (mECEQ-E)***

The Cigarette Evaluation Questionnaire was initially developed in the PI's laboratory and used in numerous studies to assess the effects of pharmacological treatments on the rewarding effects of cigarette smoking. The mCEQ-E will be utilized to assess the degree to which participants experience the reinforcing of smoking, providing five subscale scores: smoking satisfaction (satisfying, tastes good, enjoy smoking), psychological rewards (calms down, more awake, less irritable, helps concentrate, reduces hunger), aversion (dizziness, nauseated), enjoyment of respiratory tract sensations (single-item assessment), craving reduction (single-item assessment). Participants will be asked to assess the 12 items of the questionnaire on a 7-point scale, ranging from "not at all" to "extremely". These 12 items will be asked for the "first cigarette smoked", "cigarette immediately after a meal", and "all other cigarettes." The e-cigarette version of this questionnaire (mECEQ-E) will also be used.

#### 8.2.14.3 ***Shiffman-Jarvik Withdrawal Scale***

The Shiffman-Jarvik Withdrawal Scale is used to measure withdrawal symptoms and a participant's desire to smoke. This scale consists of five subscales: craving, psychological symptoms, physical symptoms, sedation, and appetite.

#### 8.2.14.4 ***Reasons to Smoke***

The Reasons to Smoke questionnaire (Appendix 17) is used to determine the most important reasons to smoke for each participant.

#### 8.2.14.5 ***FTND -- The Fagerström Test for Nicotine Dependence***

The Fagerström Test for Nicotine Dependence is a six-item questionnaire developed by Karl-Olov Fagerström and is used to determine someone's level of nicotine dependence. The scores obtained on the test allow the classification of nicotine dependence in three different levels: mild (0-3 points), moderate (4-6 points), and severe (7 -10 points).

#### 8.2.14.6 ***ABOUT – Assessment of Behavioral Outcomes***

The ABOUT is a self-report instrument that measures dependence in a directly comparable way across different tobacco- and nicotine-containing products.

#### 8.2.14.7 ***Prior and Concomitant Medication***

At each visit, participants will report any changes in medication use, including the use of supplements, vitamins, over-the-counter medications, and prescription medications.

#### 8.2.14.8 ***Smoking History Questionnaire***

The Smoking History is a questionnaire designed to help assess the participant's current and past smoking habits. This questionnaire will be administered at screening (V1) and will include questions about the number of years participants have smoked combustible cigarettes (CC), the number of CCs per day smoked over the last 12 months, brand of CCs, use of other tobacco products and use of nicotine replacement therapy or other smoking cessation treatments. This questionnaire will also be used to check eligibility criteria.

#### 8.2.14.9 ***Registration Form***

This form is an internal questionnaire designed to collect demographic information about participants. It will be administered at screening (V1).

#### **8.2.14.10 Medical History Form**

The Medical History form is an internal questionnaire designed to help assess the participant's current health and any health history. This questionnaire also includes questions about all medications (include prescription medications, other-the-counter medications or supplements) taken in the past 30 days. It is designed to help assess the participant's current health and health history and is used to help determine eligibility. This form is administered at the initial screening visit (V1).

#### **8.2.14.11 Review of Systems**

The Review of Systems is an internal questionnaire administered at screening (V1) to help assess the participant's current health and health history by asking about the presence of a list of symptoms.

#### **8.2.14.12 Employment History**

The Employment History is an internal questionnaire designed to collect information about a participants' social economic status. Participants will be presented this questionnaire after enrollment, at the second visit (V2).

#### **8.2.14.13 Medication Compliance**

Participants will be queried via SMS text messages whether they have been compliant with taking the study specific medications. These messages will commence after the second visit and continue through the End of Study.

#### **8.2.14.14 Smoking Status**

SMS text messages will be sent to participants starting after enrollment, through the End of Study, to ascertain the participants smoking status.

### **8.3 5-DAY SMOKING BASELINE COLLECTION**

After verification of eligibility (approximately two days after screening), participants will commence a five-day smoking baseline data collection. Participants will be called and given instructions on the use of the SMS system which will administer questions about smoking status in order to collect baseline data prior to start of the Halo and the study drugs.

### **8.4 6-MONTH FOLLOW UP**

Participants who complete the study will be contacted six months after the switch day utilizing an automated SMS messaging system, to ascertain their current smoking status and use of e-cigarettes. If a participant self-reports current abstinence from smoking they will be asked to return to the office for collection of an expired air CO for verification.

## 8.5 SCHEDULE OF EVENTS

Visit Assessments and Procedures		Screening Session	Baseline Cig Data Collection	Laboratory Sessions							Product Use Period
				V2	V3	V4	V5	V6	V7	13 Weeks	
		V1								PM SMS	
Informed Consent and Guidance		•									
Inclusion/Exclusion Criteria		•									
Enrollment/Randomization				•							
Prior and Concomitant Medication		•		•	•	•	•	•	•		
Questionnaires	Smoking History Questionnaire	•									
	Registration Form	•									
	Employment History			•							
	Medical History/Review of Systems	•									
	Payment Verification Form	•		•	•	•	•	•	•		
	Reasons to Smoke			•					•*		
	Modified Cigarette Evaluation Questionnaire Extended (mCEQE)			•	•	•	•	•	•		
	Modified e-Cigarette Evaluation Questionnaire Extended (meCEQE)				•	•	•	•	•		
	The Fagerström Test for Nicotine Dependence (FTND)			•	•				•		
	Shiffman-Jarvik Withdrawal Scale			•	•	•	•	•	•		
	Assessment of Behavioral OUTcomes (ABOUT)			•	•				•		
	Patient Health Questionnaire (PHQ-9)	•		•	•	•	•	•	•		
	e-Cigarette Usage and Smoking Status (via daily SMS text)			•						•	
	Medication Adherence (via daily SMS text)									•	
	Safety Laboratories		•								
Serum Pregnancy Test (Females)		•									
Urine Pregnancy Test (Females)				•	•	•	•	•	•		
Urine Drug Screen		•									
CO Breath Test		•		•	•	•	•	•	•		
ECG		•									
Vitals	Blood Pressure	•		•	•	•	•	•	•		
	Heart rate	•		•	•	•	•	•	•		
	Temperature	•									
	Respiratory rate	•		•	•	•	•	•	•		
	Weight	•		•	•	•	•	•	•		
	Height	•									
Physical Examination		•		•#	•#	•#	•#	•#	•#		
Halo Assessment and Questionnaire				•							
Collect Used/Unused Halo products					•	•	•	•	•		
Dispense Halo products				•	•	•	•	•			
Collect Used/Unused Blister Packs					•	•	•	•			
Dispense Study Drugs in Blister Packs					•	•	•	•			

# Targeted examination as needed

\* Based on current product use

## 8.6 SMS MESSAGING

8.6.1 Daily SMS Message (after screening, prior to V2) – Participants will receive a text with a link to a survey to access the following:

- Have you smoked any combustible cigarettes today?
  - If yes, how many cigarettes did you smoke?
  - What was your favorite cigarette of the day?  
1-First one, 2-One immediately after a meal, 3-Any other cigarette

8.6.2 Daily SMS Message (From Visit 2) -- Participants will receive a text with a link to a survey to assess the following:

- Have you smoked any combustible cigarettes today?
  - If yes, how many cigarettes did you smoke?
  - Which cigarette did you smoke today? (If only 1 cigarette is reported)  
1-First one of the day, 2-One immediately after a meal, 3-Any other cigarette
  - What was your favorite cigarette of the day? (Of more than 1 cigarette is reported)  
1-First one, 2-One immediately after a meal, 3-Any other cigarette
- Have you used your e-cigarette today?
  - If yes, how many times did you use your e-cigarette today?
- Did you take your study drugs this morning? (After Visit 3)

8.6.3 6-Month follow up SMS Message -- Participants will receive a text with a link to a survey to assess the following:

- Have you smoked a combustible cigarette since your last visit?
  - If yes, are you still smoking combustible cigarettes right now?
  - How many combustible cigarettes do you smoke per day on average?
- Have you used an e-cigarette since your last visit?
  - If yes, are you still using an e-cigarette?
  - How often do you use an e-cigarette?
- Have you used any other nicotine containing products (other than e-cigarettes) since you last visit?

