## 1.2 BACKGROUND

According to the U.S. Surgeon General (2010 Report), the major smoking-related diseases, including cancer, heart and lung disease, have been linked to inhaling the combustion products of burning tobacco, rather than to nicotine per se. Therefore, less toxic forms of nicotine delivery, such as e-cigarettes, offer a potential avenue for harm reduction for smokers who cannot or do not wish to relinquish their nicotine dependence. A substantial fraction of smokers who use e-cigarettes continue to smoke combustible cigarettes ("dual use"), eroding the potential beneficial impact on disease risk. Therefore, it is important to examine strategies for enhancing complete switching to e-cigarettes from combustible cigarettes. We hypothesize that dual users find it most difficult to relinquish their favorite cigarettes, which surveys indicate are those smoked after meals. We hypothesize that a specific combination of FDA-approved medications shown to promote weight loss, consisting of bupropion and zonisamide, will reduce appetite, reduce the enjoyment of cigarettes after meals, and facilitate complete switching from combustible cigarettes to e-cigarettes. In addition to the hypothesized mechanism of reducing post-meal enjoyment of smoking, bupropion is an FDA-approved smoking cessation treatment (at 150 mg b.i.d.) that reduces craving for cigarettes as well as withdrawal symptoms of irritability, which could also facilitate complete switching. Bupropion and its metabolites block reuptake of dopamine and norepinephrine, which also have anti-depressant effects.

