### 2.3 CHANGE IN REWARDING EFFECTS OF SMOKING CIGARETTES

Secondary analyses will evaluate the hypothesis that enjoyment of smoking after meals is attenuated by zonisamide/bupropion treatment. The smoking satisfaction scale of the mCEQ-E will be compared between cigarettes smoked after meals versus all others smoked during the day, examining how this difference changes after zonisamide/bupropion usage. Additionally, the proportion of participants who report smoking after meals, while reporting not smoking at other times, will be compared between the first week and the weeks after zonisamide/bupropion usage.

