12. Did you enjoy smoking?							

Please answer the following questions based on the cigarette smoked **immediately after a meal**.

- Did not smoke **immediately after a meal**: Skip section

	Not at all	Very little	A little	Moderately	A lot	Quite a lot	Extremely
1. Was it satisfying?							
2. Did it taste good?							
3. Did it make you dizzy?							
4. Did it calm you down?							
5. Did it help you concentrate?							
6. Did it make you feel more awake?							
7. Did it reduce your hunger for food?							
8. Did it make you feel nauseated?							
9. Did it make you feel less irritable?							

10. Did you enjoy the sensations of the smoke in your throat and chest?							

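### On one-cigarette days the daily text's answer options overlap, so a sole after-meal cigarette can be recorded as the first of the day and after-meal smoking can be undercounted

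*Combined protocol and SAP*

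**What the plan says.** From Visit 2 the daily text (Section 8.6.2) asks whether any combustible cigarettes were smoked that day and, if so, how many. The next question depends on the count:

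- **One cigarette:** "Which cigarette did you smoke today? (If only 1 cigarette is reported"), with the answers "1-First one of the day, 2-One immediately after a meal, 3-Any other cigarette".
- **More than one:** "What was your favorite cigarette of the day? (Of more than 1 cigarette is reported"), with similar answers. Nothing asks whether any cigarette followed a meal.

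No rule says which answer to choose when two are true, and there is no instruction to mark all that apply.

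Section 2.3 plans a secondary comparison: "the proportion of participants who report smoking after meals, while reporting not smoking at other times, will be compared between the first week". The other side of the comparison is the period on study drug. The section does not say which instrument supplies this proportion.

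The after-meal cigarette is central to the study's rationale. Section 1.2 states: "We hypothesize that dual users find it most difficult to relinquish their favorite cigarettes, which surveys indicate are those smoked after meals".

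The other place where after-meal smoking is recorded is the mCEQ-E (Appendix 9). It is completed at visits and refers to the last day smoked. It has separate blocks for the first cigarette, the after-meal cigarette and all others.

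**The concern.** The one-cigarette question is meant to say what kind of cigarette the day's only one was. On exactly those days the first option is always true, so it does not separate one kind from another. A participant whose only cigarette followed lunch can tick option 1 or option 2 and be truthful either way. If the survey keeps one answer, the after-meal information is lost whenever option 1 is ticked.

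This is also the only daily item that can show directly that a day's smoking was after a meal and at no other time. On days with two or more cigarettes, knowing the favourite does not show that the others were also after meals. If the daily texts are the source for the Section 2.3 proportion, the overlap weakens the one item able to support it. Answers already stored as option 1 could not be re-sorted later.

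**Working it through.** The plan states no figure for this item, so there is none to reproduce. The check is a logical one, followed by a misclassification range.

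**Step 1: which options can be true on a one-cigarette day, read literally**

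| Sole cigarette | Option 1 (first) | Option 2 (after a meal) | Option 3 (any other) |
|---|---|---|---|
| Smoked after a meal | true | true | not true |
| Not smoked after a meal | true | not true | not true |

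Option 1 is true in both rows. Option 2 is never true without option 1. Option 3 is never strictly true.

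**Step 2: direction of error.** An after-meal cigarette can truthfully be coded 1. A cigarette not smoked after a meal gains no reason from the overlap to be coded 2. Any error from this cause therefore lowers the after-meal count.

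**Step 3: size.** Let t be the true share of one-cigarette days on which the cigarette followed a meal, and f the fraction of those days answered with option 1. With one stored answer:

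observed share = t × (1 − f)

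The documents give neither t nor f. Both are assumptions here, with f run over its full range.

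| Assumed t | f = 0 | f = 0.25 | f = 0.5 | f = 0.75 | f = 1 |
|---|---|---|---|---|---|
| 30% | 30% | 22.5% | 15% | 7.5% | 0% |
| 50% | 50% | 37.5% | 25% | 12.5% | 0% |
| 70% | 70% | 52.5% | 35% | 17.5% | 0% |

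For example, 0.50 × (1 − 0.25) = 0.375. There is no loss only if every affected participant ticks option 2.

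**Step 4: what the range describes.** It is a share of one-cigarette days. Section 2.3 counts participants over weeks, and the plan has no rule for turning daily answers into a participant's status. The table therefore cannot be read as the bias in the Section 2.3 proportion.

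**Step 5: can the mCEQ-E stand in?** Its after-meal block opens with "Please answer the following questions based on the cigarette smoked" and specifies a cigarette right after a meal. That block has its own box for those who did not smoke then. It is filled in separately from the first-cigarette block, so a cigarette that was both can be rated in both, and the overlap does no harm there. But the form covers only the last day smoked before each visit. Its block for all other cigarettes has no box to say there were none, so it is not a clean source for after-meal-only smoking either.

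**The case against.** The strongest reply is that participants will not read option 1 literally. Since option 3 makes no sense for a sole cigarette unless option 1 means the usual morning one, the authors probably meant it that way. Section 13.1.2 describes the occasions as morning, after meals and other times, and Section 8.3 says participants are called and instructed on the SMS system. On that reading f could be low, and this stands: low values, including zero, are plausible. It does not remove the overlap. The text participants see does not mention morning, and a sole cigarette after breakfast still fits options 1 and 2.

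A second reply is that single-answer storage is not stated. That is correct. It is inferred from the numbered list and the singular question, and the survey's response format is not described.

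Three stronger readings are tempting, and the documents do not support them:

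- **Each option 1 answer from an after-meal smoker removes a case from the Section 2.3 numerator.** The plan does not name the daily text as the source, and without a rule from days to participants one answer may or may not change anyone's classification.
- **The loss falls on the on-drug weeks and so favours the study hypothesis.** Entry requires at least 10 cigarettes a day, so it is plausible that one-cigarette days are rarer early on, but no figure is given. If the first week is the one between Visits 2 and 3, participants already have the e-cigarette and their smoking level is unknown. If it is the baseline period, Section 8.6.1 does not ask this question at all. Section 2.3 also does not say which direction of change in the proportion would support the hypothesis.
- **The item is invalid.** What is shown is an ambiguity with a known direction and an unknown size.

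**Conclusion.** The overlap is real and follows from the wording alone: the question appears only when one cigarette is reported, and a sole cigarette is always the day's first. Provided one answer is stored, after-meal smoking on those days can be undercounted, with no matching reason for overcounting. For an assumed true share of 50%, the observed share lies anywhere from 50% to 0%, and the documents do not narrow this.

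The consequence is limited to the secondary after-meal proportion in Section 2.3, and only if the daily texts feed it. Imbalance between the first week and the on-drug weeks is plausible but not shown. The primary abstinence outcome, the 25/50 decision rule and the mCEQ-E satisfaction comparison do not depend on this item. The point merits correction mainly because the correction is nearly free.

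**What to change.** In Section 8.6.2, on days with one reported cigarette, replace the three options with: *Was this cigarette smoked immediately after a meal? Yes/No*. If time of day is also wanted, ask it as a separate item. State in Section 2.3 that this answer is used when deriving after-meal-only days.

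The cost is rewording one survey item and adding a sentence to the plan. Participant burden does not rise unless the optional time-of-day item is added. With the overlap gone, f is zero by construction and the observed share equals the true share apart from ordinary reporting error.

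This does not resolve days with two or more cigarettes: someone who smokes two or three, all after meals, would still not be identified from the daily text. No change to the mCEQ-E is needed.
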